17.3 STATISTICAL METHODS

17.3.1 PROPOSED STATISTICAL METHODS

Outliers: Statistical and professional analysis is used to determine whether to include outliers.

Handling of Missing Values in Primary Efficacy Endpoint Data: If a primary efficacy endpoint data point is missing for an individual subject, the method of imputation will be determined based on statistical and professional considerations. For subjects who drop out, the last observation carried forward (LOCF) method will be used.

Analysis of Incomplete Cases: Analyze the reasons for each drop-out case individually.

Descriptive Statistics: Report the mean, standard deviation, maximum value, minimum value, median, quartiles, and percentages of occurrences.

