1.1 STUDY DESIGN

Multicenter, open-label, dose-escalation, exploratory clinical research.

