4 CONTROL GROUP

The control group is not involved in the early trial.

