17.2 DEFINITION AND SELECTION OF ANALYSIS SETS

Full Analysis Set (FAS): This set includes all enrolled cases that have received the study drug. FAS is used for reporting demographic data and baseline characteristics.

Per-Protocol Set (PPS): The PPS comprises cases that meet the inclusion criteria, do not meet the exclusion criteria, and have completed the treatment protocol. In other words, it includes cases that adhered to the trial protocol, completed Case Report Forms (CRFs) or electronic Case Report Forms (eCRFs), and are suitable for analysis (PP analysis). PP analysis is primarily used for efficacy assessment.

Safety Set (SS): The SS consists of actual data with safety indicators recorded from the initiation of fiberoptic bronchial cell collection. Safety-related missing values

should not be carried forward. The SS may exclude certain cases for evaluation, such as cases exceeding the age inclusion criteria, but it does not include cases where safety assessments cannot be made due to the use of prohibited drugs. SS is used for safety evaluation analysis.

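### The per-protocol efficacy set and the LOCF rule conflict, and on either reading the uncontrolled change from baseline tends to look too favourable

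*Protocol*

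**What the plan says.** Protocol section 17.2 defines three analysis sets. The FAS holds every enrolled patient who received the product, and its one stated use is: "FAS is used for reporting demographic data and baseline characteristics". The PPS holds patients who satisfy the inclusion criteria, "do not meet the exclusion criteria, and have completed the treatment protocol"; the section adds adherence to the protocol and completed case report forms. On its use: "PP analysis is primarily used for efficacy assessment". No efficacy analysis in the FAS and no sensitivity analysis is stated.

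Section 17.3.1 deals with missing data under a label that refers to the primary efficacy endpoint. For isolated missing values, "the method of imputation will be determined based on statistical and professional considerations". For leavers, "For subjects who drop out, the last observation carried forward (LOCF) method will be used". On extreme values: "Statistical and professional analysis is used to determine whether to include outliers".

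The setting is "Multicenter, open-label, dose-escalation, exploratory clinical research" (section 1.1). Section 4 adds: "The control group is not involved in the early trial". The primary outcome in section 8.1 is safety only. FVC, DLCO and the other efficacy measures are secondary, mostly at weeks 4, 12 and 24 (section 8.2), and are summarised descriptively (section 17.3.3).

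**The concern.** The statistical analysis plan is not at hand, but these rules are fixed in the protocol, so a later plan would inherit them.

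The set and the imputation rule do not fit together, and the imputation rule names an endpoint that does not exist. A programmer could not tell from the text whether a patient who leaves at week 10 is omitted from the week-24 mean, carried forward into it, or handled by judgement.

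The choice matters because the before/after mean in each dose group is the efficacy result. Section 1 makes it a secondary purpose to assess efficacy by dose and to advise on doses for later studies. Groups hold 3 to 6 patients (section 1.3), so one leaver can shift a group mean and the comparison between doses.

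Loss need not be unrelated to outcome. Section 2.4.1 lets the investigator withdraw patients for adverse events. Section 2.4.2 treats patients whose examinations could not be carried out as withdrawn even if they have not formally left. Section 6.7 links acute exacerbation to worse lung function and high mortality.

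**Working it through.** **The conflict, from the text**

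- Reading A: the PPS needs adherence and completed forms through follow-up. Drop-outs are then outside the main efficacy set and LOCF fills nothing.
- Reading B: section 3.3 describes treatment as one administration in two stages, with follow-up coming afterwards. Completing treatment could then mean only being dosed. Drop-outs stay in and LOCF fills their later visits.
- On both readings, LOCF is attached to an endpoint type that section 8.1 does not contain.

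**Size of the error under each reading**

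The plan gives no expected decline, SD or drop-out rate, so there is no figure of its own to reproduce here. Group sizes (3 to 6) and visit weeks come from sections 1.3 and 8.2. The rest is assumed:

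- patients who stay decline linearly by D over 24 weeks;
- one of n patients leaves, and declines linearly k times as fast (k = 1, 2, 3);
- the leaver's last value is at week w = 4 or 12.

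Mean decline in units of D:

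- true: (n − 1 + k)/n
- LOCF: (n − 1 + k·w/24)/n
- PPS without the leaver: 1

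Share of the true decline that is missed:

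- LOCF: k(1 − w/24)/(n − 1 + k)
- PPS: (k − 1)/(n − 1 + k)

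Example, n = 6, k = 2, w = 4: true 7/6 = 1.167; LOCF (5 + 0.333)/6 = 0.889, so 0.278/1.167 = 24% is missed; PPS 1.000, so 0.167/1.167 = 14% is missed.

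| n | k | True mean decline (× D) | LOCF, last value week 4 | LOCF, last value week 12 | PPS |
|---|---|---|---|---|---|
| 6 | 1 | 1.00 | 14% | 8% | 0% |
| 6 | 2 | 1.17 | 24% | 14% | 14% |
| 6 | 3 | 1.33 | 31% | 19% | 25% |
| 3 | 1 | 1.00 | 28% | 17% | 0% |
| 3 | 2 | 1.33 | 42% | 25% | 25% |
| 3 | 3 | 1.67 | 50% | 30% | 40% |

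The LOCF and PPS columns belong to different readings and must not be summed.

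A second set of assumptions points the same way. Suppose patients who stay do not change and one leaver of six truly falls by 10 percentage points. The true mean is −10/6 = −1.67. The PPS gives 0. LOCF gives −0.28 (week 4) or −0.83 (week 12).

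**Outliers (minor)**

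In simulated normal samples, dropping the single worst value moves the mean by about 0.42 SD (n = 3) or 0.25 SD (n = 6). Dropping the best value moves it as far the other way.

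**The case against.** Several points weigh against a stronger claim.

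- **Stacking.** A reader might infer that the PPS and LOCF together compound the bias. They cannot both act on the same patient.
- **Completers only.** A reader might take the PPS to exclude everyone who died or worsened. Section 17.2 does not say so: a patient who worsens but attends visits stays in, and under Reading B so does a dosed leaver.
- **Outliers.** A reader might infer that the outlier rule also favours the product. It has no direction. It leaves unmasked discretion without a criterion, and the criterion could be given in the statistical analysis plan.
- **Direction.** The PPS error is zero when leavers decline like the others and would reverse if they declined more slowly. The LOCF error presumes decline over 24 weeks.
- **Last value.** The flowchart has an early-withdrawal column. Its lung-function row cannot be read in the text available. If lung function is measured there, the carried value is later and the LOCF error shrinks.
- **Hidden deterioration.** Section 17.3.1 reviews each drop-out's reasons, section 17.2 bars carrying safety values forward, section 17.3.2 reports exacerbations, and section 12.1 counts progression deaths as serious adverse events. Section 17.3.4 already requires sample sizes in tables.
- **Status.** Efficacy is secondary, exploratory and descriptive, so no test error is inflated.

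All of this stands and limits the point. None of it corrects the efficacy means by dose group. The safety tables are also an incomplete substitute, since section 12.1 exempts hospitalisation for disease progression from serious adverse event reporting.

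**Conclusion.** The point holds as a conflict between sections 17.2 and 17.3.1 and as a likely upward lean in the efficacy summaries. Sections 17.2 and 17.3.1 must be reconciled, and LOCF has no valid object as written.

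For one leaver, under assumed linear decline with k from 1 to 3, LOCF misses 8% to 31% of the mean decline in a group of six and 17% to 50% in a group of three. The PPS misses 0% to 25% and 0% to 40%. The sizes rest on these assumptions and not on figures in the protocol. The LOCF direction needs only that the outcome declines after the last visit; the PPS direction also needs leavers to decline faster than the rest.

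The documents do not support saying that deterioration is hidden from the report or that every rule favours the product. The harm is a flattering before/after summary and a distorted comparison of doses. The change should be made, but it does not threaten the primary safety objective.

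**What to change.** In section 17.2, make the FAS the efficacy set: all dosed patients, by dose group and pooled, including any who are replaced under section 1.7. Keep the PPS as a sensitivity analysis and state whether a dosed patient who leaves follow-up belongs to it.

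In section 17.3.1, delete LOCF and the reference to a primary efficacy endpoint. Show observed FVC, DLCO and other efficacy values by visit with n. List deaths and withdrawals for worsening beside each mean. A mixed model on all available data is optional and supportive only: with 15 to 24 patients it can say little about single doses, and it assumes data missing at random.

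As a minor change, keep all values in the main summary. Show any exclusion, for a documented test-quality failure, only as a sensitivity analysis.

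The cost is revised wording and slightly more programming, with no change to patients, visits or sample size. The estimates may look less favourable.

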17.3.2 SAFETY EVALUATION

Adverse events (AEs) will be recorded after the first bronchoscopy collection and following the second bronchoscopy treatment. The description of AEs after the first bronchoscopy collection and the analysis of AEs after the second bronchoscopy treatment are as follows:

(1) Calculation of the incidence and severity of cell therapy-related adverse events (AEs) for each group.

(2) Calculation of the incidence of bronchoscopy-related complications for each group.

(3) Calculation of the mean, standard deviation, median, and interquartile range for the dynamic changes of each lung tumor biomarker in all groups.

(4) Presentation of the cross-tabulation of routine safety check abnormalities (complete blood count, urinalysis, blood biochemistry, electrolytes, electrocardiogram) between baseline and each visit.

(5) Recording the frequency and severity of acute IPF exacerbations

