1 RESEARCH PURPOSE

Primary purpose: To evaluate the safety and tolerability of different doses of REGEND001 autologous therapy product for the treatment of idiopathic pulmonary fibrosis (IPF).

Secondary purpose: To assess the efficacy of different doses of REGEND001 autologous therapy product for the treatment of IPF and recommend appropriate cell therapy doses for subsequent clinical studies.

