6 SAFETY ASSESSMENTS

- Primary Endpoints:

Incidence and severity of cell therapy-related adverse events (AE) within 24 weeks post-treatment.

- Secondary Endpoints:

Incidence of complications during bronchoscopy within 24 weeks post-treatment;

Changes in pulmonary tumor markers compared to baseline at 12- and 24-weeks post-treatment;

Changes in abnormal values of routine safety checks compared to baseline within 24 weeks post-treatment (blood routine, urine routine, blood biochemistry and electrolytes, electrocardiogram).

Frequency and severity of acute IPF exacerbation events within 24 weeks post-treatment.

Corresponding indicators will be tested during follow-up observation, as follows.

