6.6 COMPLICATIONS OF BRONCHOSCOPY

Common complications of bronchoscopy include anesthesia accidents, bleeding, pneumothorax, laryngospasm, hypoxemia, infection, post-procedural fever, and other unforeseen events.

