8 OUTCOME MEASURES

8.1 PRIMARY OUTCOME MEASURES

Incidence and severity of the cell therapy-related adverse events (AEs) within 24 weeks after treatment.

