11.2 COLLECTION AND RECORDING OF ADVERSE EVENTS

Monitoring of Adverse Events (AE) will be conducted throughout the entire study, and it is the responsibility of the investigators to record all AEs observed during the study period. Any adverse medical events occurring from the initiation of autologous cell collection until the end of follow-up, regardless of severity or causal relationship with the investigational drug, must be documented in the medical records. Detailed documentation of the following information is required for all AEs:

- **AE Description:** Describe the AE using medical terminology rather than the language reported by the subjects. If applicable, include symptoms, signs, abnormal laboratory findings, and diagnosis. If the same AE occurs more than once in a subject and the subject has recovered between the two events, each occurrence should be recorded separately.

- **AE Onset Date:** The date when the subject first experienced the AE or when symptoms related to the AE appeared. If the AE is a clinically significant abnormal laboratory finding or test result, the date of sampling should be recorded.
- **AE Outcome Date:** The date of resolution of the AE or when symptoms related to the AE improved. If the AE is still ongoing, the outcome date does not need to be filled.
- **Severity of AE.**
- **Causal Relationship between AE and the investigational drug.**
- **Actions Taken:** (1) Actions taken with regard to the investigational drug: continued use, discontinued use, treatment completed, not applicable; (2) Actions taken regarding the AE: none, medication treatment, non-drug treatment.
- **Outcome of AE:** Disappeared, recovery with sequelae, improvement, stable, aggravated, death, subject refusal for follow-up or lost to follow-up, unknow.

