12.2 COLLECTION AND RECORDING OF SERIOUS ADVERSE EVENTS

This study should record serious adverse events (SAEs) from the start of autologous cell collection until the end of follow-up.

If a subject experiences a serious adverse event (SAE) during the trial, regardless of its relationship to the investigational drug, the investigator should immediately take appropriate treatment measures to ensure the subject's safety and promptly report to the clinical trial responsible person of the study sponsor. Upon learning of an SAE, the investigator must immediately inform the

sponsor and/or Contract Research Organization (CRO), and the medical personnel of the sponsor and/or CRO should review the content of the SAE report form and provide feedback to the investigator. After multiple confirmations and reviews, the investigator signs and dates the report.

For SAEs with temporarily incomplete or uncertain information, it should still be reported to the sponsor and/or CRO personnel in a timely manner based on the principles of Good Clinical Practice (GCP), and supplementary reports should be provided in the form of follow-up reports once more information becomes available. The narrative section of the SAE report should provide detailed descriptions of the symptoms, severity, occurrence and management time, measures taken, follow-up time and method, as well as the outcome of the SAE. All SAEs should also be recorded in the Case Report Form (CRF), and the information provided in the SAE report form must be consistent with the data recorded in the CRF for the corresponding event.

If the investigator is unsure whether an adverse event (AE) qualifies as an SAE, it should be considered as an SAE until its nature can be determined. Such events should be promptly reported to the sponsor and/or CRO personnel in accordance with the principles of GCP.

Any deaths occurring during the trial, regardless of their relationship to the investigational drug, including deaths not related to the studied disease progression, require the investigator to provide timely rescue measures and submit necessary information, such as autopsy reports and final medical reports, to the sponsor and ethics committee.

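### The primary endpoint and the only general adverse-event analysis count only events judged cell therapy-related, so the main safety result of an open-label, uncontrolled trial depends on unblinded attribution

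*Protocol*

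**What the plan says.** The primary purpose in section 1 is "To evaluate the safety and tolerability of different doses of REGEND001 autologous therapy product". Section 1.1 makes the trial open-label, and section 4 says "The control group is not involved in the early trial".

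The primary endpoint is defined twice, with the same restriction each time: "Incidence and severity of cell therapy-related adverse events (AE) within 24 weeks post-treatment" in section 6 and "Incidence and severity of the cell therapy-related adverse events (AEs) within 24 weeks after treatment" in section 8.1. Item (1) of section 17.3.2 carries it into the analysis: "Calculation of the incidence and severity of cell therapy-related adverse events (AEs) for each group". The other four items there cover bronchoscopy complications, tumour markers, shifts in routine laboratory and ECG findings, and acute IPF exacerbations.

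Collection is wider. Under section 11.2, AEs from the start of cell collection to the end of follow-up, "regardless of severity or causal relationship with the investigational drug, must be documented in the medical records". Section 12.2 records serious adverse events (SAEs) over the same period and requires follow-through on "Any deaths occurring during the trial, regardless of their relationship to the investigational drug".

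**The concern.** The protocol collects every AE but builds its main safety result from those that pass a causality judgement. In a controlled, blinded trial a reader could compare all-cause rates between arms and so bypass individual attribution. Here there is no other arm, and the people who attribute know the treatment and the dose. If the judgement errs towards unrelated in some cases, the primary result understates the events at that dose, and nothing in the listed outcomes shows how many events were set aside.

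What is at stake is how the reported safety result can be read, in a trial whose primary purpose is safety and tolerability by dose.

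**Working it through.** **1. Which events reach a listed summary**

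| Class of event | Filter on cell causality | Listed summary |
|---|---|---|
| AEs judged cell therapy-related | Yes | 6, 8.1, 17.3.2 (1), by group |
| Bronchoscopy complications | No | 6, 8.2, 17.3.2 (2), by group |
| Tumour markers | No | 6, 8.2, 17.3.2 (3) |
| Laboratory and ECG abnormalities | No | 6, 8.2, 17.3.2 (4) |
| Acute IPF exacerbations | No | 6, 8.2, 17.3.2 (5) |
| Other AEs judged unrelated, including SAEs and deaths | Left out by the filter in row 1 | None listed |

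Section 8.2 has 13 outcomes. Six are efficacy measures (DLCO, FVC, DLCO/VA, walk test, SGRQ, HRCT), which leaves 13 − 6 = 7 on safety. None of these 7, and none of the 5 items in 17.3.2, is an all-cause count of AEs, SAEs or deaths.

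**2. The period before dosing**

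The lead-in to 17.3.2 promises a description of AEs after the first bronchoscopy, when no cells have yet been given. Item (1) can hardly capture these. Item (2) covers only those that are procedure complications.

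**3. How firm the attribution can be**

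- Two of the five factors in section 11.4 ask what happens on stopping or reducing the drug and on giving it again. Treatment is a single administration (1.3, 3.3), so neither can inform the judgement.
- The category for possibly unrelated events in 11.4 accepts a plausible time course but applies where the event does not match known reactions. Section 15.2.3 reports no study-related complications in earlier research, so there is little known profile to match. A new toxicity with plausible timing could therefore be placed there. This is not inevitable, because the category for probably related events does not ask for prior support.

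**4. How often the last row of the table might matter**

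The planned sample size reproduces from the group sizes in 1.3: 3 + 3 + 3 + 6 = 15 and 6 + 6 + 6 + 6 = 24. The protocol gives no rate for the affected events, so the per-patient risk p below is assumed. The chance of at least one affected patient is 1 − (1 − p)^n:

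| Assumed p | n = 15 | n = 24 |
|---|---|---|
| 1% | 14.0% | 21.4% |
| 2% | 26.1% | 38.4% |
| 5% | 53.7% | 70.8% |
| 10% | 79.4% | 92.0% |

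For example, with p = 5% and n = 15, 1 − 0.95^15 = 0.537. One such event would be 1/3 = 33% of a group of 3 or 1/6 = 17% of a group of 6. These figures show only that the case is not far-fetched under some assumptions. They do not measure bias.

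**The case against.** **Routine tables belong in the statistical analysis plan.** All-cause, SAE and death tables are commonly specified there, that plan is not shown, and 17.3.2 does not say its list is complete. This stands: the absence of such tables is not in itself a fault of the protocol. It does not remove the point, because the related-only primary endpoint and item (1) are fixed in the protocol.

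**A related-AE endpoint is a legitimate choice.** It matches the escalation rules in 1.6 (1) and (2), where the three upper causality categories count as related. Events for which disease progression cannot be excluded fall within the possibly related category of 11.4, so much doubtful attribution lands on the related side. This also stands and narrows the exposure. Section 8.1 does not restate the mapping, but nothing suggests a different one.

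**Few events are left over.** Section 6.6 is broad: "Common complications of bronchoscopy include anesthesia accidents, bleeding, pneumothorax, laryngospasm, hypoxemia, infection, post-procedural fever, and other unforeseen events". With exacerbations and laboratory/ECG findings also unfiltered, a large part of what is likely in this population is reported anyway.

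**Small groups make rates a weak check.** One event in 3 patients has an exact 95% interval of about 1% to 91%, and one in 6 about 0.4% to 64%. An all-cause rate by dose cannot test attribution formally. Its use is to show what was set aside, so that a reader knows which narratives to look at.

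**Two stronger readings are tempting.** A reader might infer that SAEs or deaths judged unrelated disappear. The documents do not support this: section 12.2 requires a narrative, an entry in the case report form and a report to the sponsor or its contract organisation for SAEs, and information to the sponsor and ethics committee for deaths. Section 17.3.1 also has each drop-out reviewed individually. A reader might also infer that escalation could go ahead over events labelled unrelated. Section 1.6 (3) lets the investigator and sponsor stop for AEs of any grade or reason.

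**Conclusion.** The point holds in a limited form. The protocol fixes a primary endpoint and a single general AE analysis that depend on unblinded attribution of single cases, with no control group and with a causality scale that partly does not suit a single administration. The effect is confined to the reported result for events judged unrelated that are not bronchoscopy complications, acute exacerbations or laboratory/ECG abnormalities. Collection, individual case reporting and the power to stop escalation are intact.

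No size of bias can be stated, because the documents give no rate for these events. The percentages in the working rest wholly on assumed risks and should not be read as an estimate of under-reporting. The importance is minor to moderate: a cheap improvement to the main safety result, with no error rate or sample size affected.

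**What to change.** In 17.3.2 item (1), and preferably in 6 and 8.1 as well:

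- Report incidence and severity of all AEs from cell administration to week 24, by dose group.
- Show SAEs and deaths separately.
- Give cell therapy-related AEs as a subset, and state which categories of 11.4 count as related.
- Tabulate AEs between cell collection and dosing separately.

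Leave section 1.6 unchanged.

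The cost is a few descriptive tables from data already collected under 11.2 and 12.2. The downside is a higher headline AE rate that includes background IPF events. The related subset beside it keeps that rate interpretable. For SAEs the increase is limited, because 12.1 (4) already keeps hospitalisation for disease progression out of SAE reports, although deaths from progression remain in.
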